ascites, muscle spasms, pruritus, abdominal pain, anemia, depression, nasopharyngitis, abdominal pain upper, arthralgia, dyspnea, pyrexia, and rash.

In a study to characterize the pharmacokinetics of rifaximin in healthy subjects, administration of a single 550 mg oral dose to fasted and fed subjects resulted in mean AUC values of 11.1 ng.h/mL and 22.5 ng.h/mL, respectively. Multiple-dose twice daily (BID) or 3 times daily (TID) regimens in healthy subjects resulted in mean AUC values of 12.3 ng.h/mL (AUCtau, steady-state), and 9.3 ng.h/mL (AUCtau, steady-state), respectively (RFPK1007). Subjects with non-C IBS had mean AUCtau values following a single dose and multiple TID doses of 9.69 ng.h/mL and 16.0 ng.h/mL, respectively, reflecting an accumulation ratio (Rc; multiple-dose AUCtau/single-dose AUCtau) of 1.77 (RFPK1010). In subjects with hepatic impairment, systemic exposure is higher than that observed in healthy subjects. Following repeat dosing of a 550 mg BID regimen in hepatic impaired subjects in RFHE3002PK, mean steady-state AUCtau values of 118 ng.h/mL, 161 ng.h/mL, and 246 ng.h/mL were observed in Child-Pugh A, Child Pugh B, and Child-Pugh C subjects, respectively. In a study to determine the effect of P-glycoprotein inhibition on the pharmacokinetics of rifaximin, an in vitro substrate of P-glycoprotein, healthy subjects received a single oral dose of rifaximin 550 mg with or without a single oral 600 mg dose of cyclosporine, a potent P-glycoprotein inhibitor (RFDI1045). Systemic rifaximin exposure (as measured by plasma Cmax and AUC0- ∞) was increased following co-administration of rifaximin with cyclosporine in this study; mean Cmax was 40.0 ng/mL and mean AUC0-∞ was 314 ng.hr/mL following single doses of rifaximin plus cyclosporine compared with mean Cmax of 0.48 ng/mL and mean AUC0- ∞ of 2.53 ng.hr/mL following single-dose rifaximin alone. While the effect of the combination of hepatic impairment and P-glycoprotein on rifaximin pharmacokinetics has not been examined, a nonclinical toxicology study in dogs (BQG0004) provides greater than 30-fold and greater than 24-fold safety exposure margins over the mean exposures for the Pglycoprotein and hepatic impairment effects, respectively.

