7.1.2 Hepatic Impairment Subject Exclusion Criteria

A subject will **not** be eligible for inclusion in this study if any of the following criteria are met:

- 1. Subject has known allergy to rifaximin, rifampin, or other rifamycins, or to excipients and/or vehicles used in the formulation or other clinically significant allergies.
- 2. Subject has participated in an investigational drug or device study within the 30 days prior to Day 1 (Baseline).
- 3. Subject is an employee of the site that is directly involved in the management, administration, or support of this study or is an immediate family member of the same.
- 4. Subject has any concurrent illness (other than liver cirrhosis), disability or circumstance that may affect the interpretation of clinical data, could cause noncompliance with treatment or visits or otherwise contraindicates participation in this study in the opinion of the investigator.
- 5. Subject is pregnant or at risk of pregnancy, or is lactating.

- 6. Subject has a history of tuberculosis infection or has received treatment for a tuberculosis infection. To rule out tuberculosis infection, any one of the following criteria must apply: a) negative tuberculin skin test or negative tuberculosis blood test or b) if a subject has had a previous positive test, they must have a current negative chest X-ray (within 6 months of enrollment), or a current negative blood tuberculosis test.
- 7. Subject is positive for human immunodeficiency virus (HIV), hepatitis B and/or hepatitis C on Screening assessments.
- 8. Subject has been diagnosed with chronic respiratory insufficiency that in the opinion of the investigator would prevent completion of the study, interfere with analysis of study results, or negatively impact the subject's participation in the study.
- 9. Subject has renal insufficiency requiring routine dialysis.
- 10. Subject has an active spontaneous bacterial peritonitis infection or subject requires daily prophylactic antibiotic therapy.
- 11. Subject shows presence of intestinal obstruction or has inflammatory bowel disease.
- 12. Subject has an active malignancy within the last 5 years (exceptions basal cell carcinomas of the skin, or if female, in situ cervical carcinoma that has been surgically excised).
- 13. Subject has current GI bleeding or has had a GI hemorrhage of sufficient severity to require hospitalization and a transfusion of ≥ 2 units of blood within 3 months prior to Screening.

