- 14. Subject is anemic, as defined by hemoglobin of $\leq 8 \text{ g/dL}$.
- 15. Subject has significant hypovolemia, or any electrolyte abnormality that can affect mental function (e.g., serum sodium <125 mmol/L, serum calcium >10 mg/dL).
- 16. Subject has severe hypokalemia as defined by a serum potassium level <2.5 mmol/L.
- 17. Subject's current, required medications are prohibited concurrent medications per protocol. Subjects will discontinue non-study rifaximin on Day -1 and will only use rifaximin provided as study drug by the sponsor during the Treatment Period through CRU discharge.
- 18. Subject is positive for *Clostridium difficile* toxin via stool examination at Screening. NOTE: Results of stool tests must be confirmed as negative for Toxins A and B prior

to Day -1. A stool sample must be collected during the Screening Period. Testing will be performed by enzyme immunoassay (EIA).

- 19. Subject has an acute illness within 1 week of CRU admission.
- 20. Subject has donated plasma within 7 days of drug administration.
- 21. Subject has donated 1 or more pints of blood (or equivalent blood loss) within 30 days prior to drug administration.
- 22. The subject has known or suspected illicit drug use within the past year, or positive findings on urine drug screen (except for allowed prescription medications), or has used any tobacco or nicotine products during the 6 months prior to screening and does not agree to refrain from using tobacco or nicotine products during the study.
- 23. The subject has received any type of vaccination within 7 days of drug administration.
- 24. Subject reports consumption of more than 2 alcoholic drinks daily, more than 14 alcoholic drinks within 14 days before the screening evaluation (an alcoholic drink is defined as 1.5 oz liquor, one 12 oz can of beer, or 5 oz of wine), or consumption of any alcohol within 24 hours of first drug administration.
- 25. The subject has consumed grapefruit juice, grapefruits, or Seville oranges within 24 hours of first drug administration and does not agree to refrain from consuming these foods during the study.

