 - d. Absolute neutrophil count, or lymphocyte count ≤ 500 cells/ μ L.
- 13. Subject has known or suspected illicit drug use within the past year, or positive findings on urine drug screen, or has used any tobacco or nicotine products during the 6 months prior to screening and does not agree to refrain from using tobacco or nicotine products during the study.
- 14. Subject has received any type of vaccination within 7 days of drug administration.
- 15. Subject reports consumption of more than 2 alcoholic drinks daily, more than 14 alcoholic drinks within 14 days before the screening evaluation (an alcoholic drink is

Clinical Study Protocol Amendment 1 08Oct2018

defined as 1.5 oz liquor, one 12 oz can of beer, or 5 oz of wine), or consumption of any alcohol within 24 hours of first drug administration.

- 16. Subject has consumed grapefruit juice, grapefruits, or Seville oranges within 24 hours of first drug administration and does not agree to refrain from consuming these foods during the study.
- 17. Subject has consumed foods and substances that are known to inhibit and/or induce cytochrome P450 (CYP) or P-glycoprotein within 24 hours of first drug administration and does not agree to refrain from consuming these foods during the study, and/or has received treatment with any drugs known to be P-glycoprotein or CYP enzyme inducers or inhibitors within 30 days prior to first drug administration (see Appendix 2 or http://medicine.iupui.edu/flockhart/table.htm for a complete listing of excluded potential CYP inducers/inhibitors).
- 18. Subject has a history of Gilbert's disease or cholecystectomy.

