8.3 Concomitant Medications and Therapies

Subjects are not to take any medications (prescription or over the counter), alternative therapy(ies), or herbal supplement(s) during this study (14 days prior to dosing through endof study), unless the investigator, after discussion with the medical monitor (if feasible), determines use of medication is required; contraceptives are allowed during this study as defined in inclusion criterion. All medications, alternative therapy(ies), and/or herbal supplement(s) used during Screening and any ongoing or new medications / therapies taken while the subject is participating in the study will be recorded in the source documents (drug name, start and stop dates, and indication) and on the appropriate page of the electronic case report form (CRF).

For hepatically impaired subjects, stable doses of the following medications will be allowed during the study:

- Stable dose of antidepressants
- Stable opioid regimen. Stable regimen includes dose, pattern of use (e.g., as needed [PRN] or chronic dosing) combinations of opioids, and route of administration (e.g., oral or transdermal administration; parenteral administration is prohibited) for at least 4 weeks prior to Visit 2 (Baseline). The dose and regimen of opioid(s) should remain unchanged (i.e., < 20% change in dose and no change in opioid[s]) throughout the trial).
- Subjects who require concomitant antibiotic therapy with a once per week dosing regimen (e.g., ciprofloxacin 500-750 mg dose/week) for spontaneous bacterial

Clinical Study Protocol Amendment 1 08Oct2018 peritonitis (SBP) may participate in the study if they started their therapy at least 1 month prior to Visit 1 (Screening).

- Neurontin (gabapentin) and Lyrica (pregabalin) if a stable dose has been taken for at least 2 months prior to Visit 1 (Screening) and the dosage is expected to remain unchanged throughout the trial.
- Laxatives or stool softeners will be allowed to treat constipation at the discretion of the investigator but should be used sparingly to avoid diarrhea.

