8.3.1 Prohibited Therapy

Use of the following medications is prohibited within the inclusion/exclusion specified prestudy timeframes and throughout the study unless otherwise noted:

- Milk thistle within 30 days of Day 1 (Baseline).
- Investigational drugs within 30 days of Day 1 (Baseline).
- Daily prophylactic antibiotics within 30 days of Day 1 (Baseline).

The following concomitant medications are prohibited after Screening and throughout the study:

- Non-study rifaximin (200 mg or 550 mg tablets) is prohibited beginning Day 1 and throughout the Treatment Period. Subjects may resume their prescription rifaximin use following CRU discharge.
- Psychoactive, neuroactive agents (except as allowed per protocol) and psychotropic drugs.
- Warfarin-type anticoagulants.
- Rifampin or other rifamycin derivatives (except study drug).
- Alternative, herbal or complementary therapies for liver cirrhosis other than those required to manage fluid and electrolyte homeostasis.

Consumption of certain foods and substances that are known to inhibit and/or induce CYP are not permitted during this study as specified in exclusion criteria. (See Appendix 16.2 or http://medicine.iupui.edu/clinpharm/ddis/main-table for a complete listing of excluded potential CYP inducers/inhibitors).

All over the counter and prescription medications are prohibited for healthy subjects. If any medication is required during the study for healthy subjects, the subject may be discontinued from the study at the discretion of the Investigator or the Sponsor.

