16.2 CYTOCHROME P450 ENZYME INDUCER/INHIBITOR COMPOUNDS*

Inducers								
1A2	2C19	2C9	2D6	2E1	3A4,5,7			
broccoli	carbamazepine	rifampin	dexamethasone	ethanol	efavirenz			
brussel sprouts	norethindrone	secobarbital	rifampin	isoniazid	nevirapine			
char-grilled meat	prednisone				barbiturates			
insulin	rifampin				carbamazepine			
Methyl					glucocorticoids			
cholanthrene					phenobarbital			
nafcillin					phenytoin			
beta- naphthoflavone					pioglitazone			
omeprazole					rifampin			
tobacco					St. John's Wort			
					troglitazone			
	Inhibitors							
1A2	2C19	2C9	2D6	2E 1	3A4,5,7			
amiodarone	cimetidine	amiodarone	amiodarone	disulfiram	delaviridine			
cimetidine	felbamate	fluconazole	celecoxib	diethyl- dithiocarbamate	indinavir			
fluoroquinolones	fluoxetine	fluvastatin	chlorpheniramine		nelfinavir			
fluvoxamine	fluvoxamine	fluvoxamine	cimetidine		ritonavir			
furafylline	indomethacin	isoniazid	clomipramine		saquinavir			
Interferon	ketoconazole	lovastatin	cocaine		amiodarone			
methoxsalen	lansoprazole	paroxetine	doxorubicin		cimetidine			
mibefradil	omeprazole	phenylbutazone	fluoxetine		ciprofloxacin			
ticlopidine	paroxetine	probenicid	halofantrine		clarithromycin			
	probenicid	sertraline	haloperidol		diltiazem			
	ticlopidine	sulfaphenazole	levomepromazine		erythromycin			
	topiramate	teniposide	methadone		fluconazole			
		trimethoprim	mibefradil		fluvoxamine			
		zafirlukast	moclobemide		gestodene ++			
			paroxetine		grapefruit juice			
			quinidine		itraconazole			
			ranitidine		ketoconazole			
			ritonavir		mifepristone			
			terbinafine		nefazodone			
					norfloxacin			

*Adapted from ht	tp://medicine.iu	pui.edu/clinj	pharm/ddis/main-ta	able

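### P-glycoprotein inhibitors are barred for healthy volunteers but not specifically for impaired subjects, so a user could inflate the impaired/healthy ratio with no stated analysis to show it

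*Combined protocol and SAP*

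**What the plan says.** **Healthy subjects.** Criterion 17 of Section 7.2.2 excludes anyone who has "received treatment with any drugs known to be P-glycoprotein or CYP enzyme inducers or inhibitors within 30 days prior to first drug administration". Section 8.3.1 adds: "All over the counter and prescription medications are prohibited for healthy subjects".

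**Impaired subjects.** Section 8.3 bars all medication from 14 days before dosing, with an exception for any drug "unless the investigator, after discussion with the medical monitor (if feasible), determines use of medication is required". It also lists classes allowed to this group, most of them on stable-dose terms. Three further provisions bear on the point:

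- Criterion 4 of Section 7.1.2 lets the investigator exclude for an illness other than cirrhosis, or a "disability or circumstance that may affect the interpretation of clinical data".
- Criterion 17 of Section 7.1.2 excludes a subject whose "current, required medications are prohibited concurrent medications per protocol". This sends the reader back to the prohibited list.
- That list, in Section 8.3.1, names rifampin and other rifamycins but not P-gp inhibitors. Its closing sentence covers foods and substances "known to inhibit and/or induce CYP are not permitted during this study as specified in exclusion criteria" and points to Appendix 16.2 or a web table. The appendix is titled "CYTOCHROME P450 ENZYME INDUCER/INHIBITOR COMPOUNDS".

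**Known effect.** Section 4.2.1 describes healthy subjects given a single 550 mg rifaximin dose "with or without a single oral 600 mg dose of cyclosporine, a potent P-glycoprotein inhibitor". It reports much higher exposure with the inhibitor and says its combination with hepatic impairment has not been studied.

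**Analysis.** Section 12.6.1 reads the hepatic effect from the 90% interval of the impaired/healthy ratio of log-transformed Cmax and AUCtau. Section 12.7.1 plans no covariate adjustment. The PK population in Section 12.3 has no exclusion for interacting drugs, and Section 12.6.3.5 only counts concomitant drugs.

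**The concern.** The protocol treats P-gp as important enough to screen out of the reference group, and reports that one potent inhibitor changes rifaximin exposure by more than hepatic impairment does. The matching restriction is absent from the group in the numerator. An investigator following the text exactly could find a P-gp inhibitor medically required and enrol the subject.

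That subject's concentrations would reflect two causes, both attributed to the liver. The ratio would rise and, because one outlying value also inflates the residual variance, the interval would widen. What is at stake is the size of the ratio and the descriptive summaries of the two MELD strata, which are the subject of the primary objective (Section 5.1).

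**Working it through.** **Inputs from the documents.** Group sizes are 12 impaired (at least 6 with MELD >25) and 6 healthy (Section 6.1). Mean exposures with and without cyclosporine, in healthy subjects after a single dose, are AUC 314 and 2.53 ng·h/mL and Cmax 40.0 and 0.48 ng/mL (Section 4.2.1). Steady-state AUCtau is 12.3 in healthy subjects and 246 in Child-Pugh C (Section 4.2.1). The earlier hepatic sub-study gave 11-fold AUCtau and 6-fold Cmax (Section 4.3). The protocol has no power calculation to reproduce.

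**Assumptions.** The number of users, the fold-effect in an impaired subject and the between-subject CV are not given. I take Section 12.6.1 to mean a pooled 12 v 6 comparison, and take 6 per MELD stratum.

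**Step 1: the two effects.** Inhibitor: 314/2.53 = 124 for AUC and 40.0/0.48 = 83 for Cmax. Hepatic impairment: 11-fold and 6-fold as reported, or 246/12.3 = 20 for Child-Pugh C AUCtau.

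**Step 2: a document-based low case.** Suppose an inhibitor could lift an impaired subject only from the Child-Pugh C mean to the level of healthy subjects on cyclosporine. The fold is then 314/246 = 1.28. This is a cross-study figure.

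**Step 3: shift in the point estimate.** If k of n impaired subjects have exposure multiplied by f, the geometric mean, and so the ratio, is multiplied by f^(k/n).

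**Step 4: shift in the upper 90% limit.** Log-scale variance is s² = ln(1 + CV²). With k users its expectation rises by ln(f)² × k(12 − k)/12/16. The half-width is t(0.95, 16) × s × √(1/12 + 1/6) = 0.873 s. Example with CV 60%, f = 5, k = 1: s goes from 0.555 to 0.675 and the interval factor from 1.62 to 1.80, so the upper limit is multiplied by 1.144 × 1.803/1.623 = 1.27.

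| Assumed fold, one user | Point ratio, 1 of 12 | MELD-stratum geometric mean, 1 of 6 | Upper 90% limit, CV 40 / 60 / 80% |
|---|---|---|---|
| 1.28 | 1.02 | 1.04 | 1.02 / 1.02 / 1.02 |
| 2 | 1.06 | 1.12 | 1.09 / 1.08 / 1.08 |
| 5 | 1.14 | 1.31 | 1.31 / 1.27 / 1.25 |
| 10 | 1.21 | 1.47 | 1.56 / 1.48 / 1.43 |

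Two users of 12 give point shifts of 1.12, 1.31 and 1.47 at 2-, 5- and 10-fold. On an expected AUC ratio of 20, one 5-fold user gives 20 × 1.144 = 22.9. If the full healthy-subject 124-fold carried over, one user of 12 would give 1.49.

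**The case against.** The strongest reply is that impaired subjects are not unprotected. Section 8.3 bars every drug by default, the exception needs a finding of medical need, and criterion 4 of Section 7.1.2 allows exclusion on judgement. Nothing indicates that any user would enrol. This stands, and it is why the concern is conditional. It does not close the gap, because neither provision contains a P-gp rule and discussion with the medical monitor is required only if feasible.

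The effect may also be small. The 124-fold figure rests on a baseline AUC of 2.53; another fasted single-dose study in Section 4.2.1 gives 11.1, and 314/11.1 = 28. The 1.28 case gives a shift of only 2%. A shift from 20 to 22.9 lies well inside a 90% interval of about 12.3 to 32.5 at CV 60%. In simulation with log-SD 0.6 and one 5-fold user of 12, the interval still covered the user-free ratio 92.5% of the time, because the extra variance widens it. So interval coverage does not fail in that case; the harm is an upward shift and lost precision. No dosing threshold is tied to the interval.

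A separate SAP is promised (Section 12) and could add a rule, but it need only be final before database lock. Samples go for assay subject by subject (Section 10.2). A reader might infer that concentrations will be seen before the rule is set, but that section covers shipment, not release of results.

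Other readings go further than the documents allow:

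- **Inducers would lower the ratio.** No inducer data on rifaximin are given.
- **The permitted weekly ciprofloxacin or antidepressants distort the result.** The documents show no effect of these drugs, or of CYP inhibition, on rifaximin exposure.
- **The CYP provision cannot reach cyclosporine.** It is absent from Appendix 16.2, but Section 8.3.1 also cites a web table that is not reproduced.

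**Conclusion.** The concern holds as a conditional one. The restriction differs between groups in the text, the protocol itself reports a large P-gp inhibitor effect in healthy subjects, and no analysis stated in the protocol would separate inhibitor use from hepatic impairment.

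Its size is unknown. It is zero with no users; with one user of 12 it is a point shift of 1.02 to 1.21 over assumed folds of 1.28 to 10. In a MELD stratum of 6 the corresponding range is 1.04 to 1.47. It would be tempting to apply the 124-fold effect to impaired subjects, but Section 4.2.1 says the combination has not been examined, so that figure is not an estimate for them.

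Nor do the documents suggest that the conclusion of higher exposure in impairment is in danger: the hepatic effect already reported is 11-fold or more for AUC. The change is worth making because it is cheap and protects the size of the ratio, which is what the study measures.

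**What to change.** 1. Add to Section 8.3.1 a prohibition of strong P-gp inhibitors, such as cyclosporine, for impaired subjects from 30 days before Day 1 through the Day 8 sample. Criterion 17 of Section 7.1.2 then excludes a candidate who needs one, so nobody has to stop a required drug. State which drugs count, since Appendix 16.2 lists CYP compounds only.
2. From the drug names and dates already recorded under Section 8.3, flag any P-gp inhibitor user before concentrations are reviewed.
3. Prespecify in the SAP a repeat of the pooled Cmax and AUCtau ANOVA without flagged users, and identify them in the MELD-stratum summaries. If there are none, say so and omit the table.

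The cost is short wording, one derived flag and at most one extra table, with no added visits, samples or subjects. A few candidates may be excluded. The sensitivity estimate is imprecise but little worse than the main one. In units of s, the log-scale half-width is 0.873 for 12 v 6, 0.890 for 11 v 6, 0.910 for 10 v 6 and 0.933 for 9 v 6, so removing one, two or three users widens it by 2%, 4% or 7% at the same SD.

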8.3.1 Prohibited Therapy

Use of the following medications is prohibited within the inclusion/exclusion specified prestudy timeframes and throughout the study unless otherwise noted:

- Milk thistle within 30 days of Day 1 (Baseline).
- Investigational drugs within 30 days of Day 1 (Baseline).
- Daily prophylactic antibiotics within 30 days of Day 1 (Baseline).

The following concomitant medications are prohibited after Screening and throughout the study:

- Non-study rifaximin (200 mg or 550 mg tablets) is prohibited beginning Day 1 and throughout the Treatment Period. Subjects may resume their prescription rifaximin use following CRU discharge.
- Psychoactive, neuroactive agents (except as allowed per protocol) and psychotropic drugs.
- Warfarin-type anticoagulants.
- Rifampin or other rifamycin derivatives (except study drug).
- Alternative, herbal or complementary therapies for liver cirrhosis other than those required to manage fluid and electrolyte homeostasis.

Consumption of certain foods and substances that are known to inhibit and/or induce CYP are not permitted during this study as specified in exclusion criteria. (See Appendix 16.2 or http://medicine.iupui.edu/clinpharm/ddis/main-table for a complete listing of excluded potential CYP inducers/inhibitors).

All over the counter and prescription medications are prohibited for healthy subjects. If any medication is required during the study for healthy subjects, the subject may be discontinued from the study at the discretion of the Investigator or the Sponsor.

